## 2.0 Study Summary

Study Title	A comparison between TiNbTaZr (GUMMETAL) and stainless-steel alloy for space closure with sliding mechanics A pilot randomized clinical trial
Study Design	Pilot randomized clinical trial
Primary Objective	1. Evaluate the total amount of canine retraction (mm) using GUMMETAL and Stainless-steel archwires 2. Evaluate the rate of canine retraction (mm/month) from T 0 -T 4 .
Secondary Objective(s)	3. Assess the 3-Dimensional control of canines during retraction from T 0 -T 4 .
Research Intervention(s)/Investigational Agent(s)	Orthodontic archwires: GUMMETAL vs. Stainless-Steel
IND/IDE #	N/A
Study Population	12-17Y11M male and female patients
Sample Size	16
Study Duration for individual participants	4 months

Study Specific Abbreviations/ Definitions	TiNbTaZr = GUMMETAL SS = Stainless Steel NiTi = Nickel Titanium
--	---

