## 6.0 Study Design\*

6.1 *Describe and explain the study design (e.g. case-control, cross-sectional, ethnographic, experimental, interventional, longitudinal, observational).*

Response: This will be a randomized pilot split-mouth clinical trial of patients with spaces  $\geq$  3mm distal to the maxillary canines in need of closure through sliding mechanics. The sample consists of adolescent patients regardless of Angle's molar malocclusion who are receiving comprehensive full fixed appliance orthodontic treatment. Preformed conjoint archwires half being GUMMETAL and the other half SS, will be utilized. Each patient will have one side of the maxilla randomly allocated into the SS or GUMMETAL treatment group. The study will follow a split-mouth design to reduce the confounding variables from patient to patient on space closure mechanics. The maxillary arch in each subject will be randomized into a SS side or GM side using a random number

generator. Spaces will be measured at; T0 is initial records, T1 is initiation of space closure, T2 will be 4 weeks after the initiation of space closure, T3 is another 4 weeks of space closure evaluation and T4 will be the final evaluation of space closure after 4 weeks from T3, via 3D intraoral scans of maxillary arches. Space measurement and calculations will utilize 3Shape software to measure the distance of canine movement based off the distal surface. Sliding mechanics will be activated through NiTi coil springs from the maxillary canines to the maxillary molars. The force will be standardized to 150 gms and will be measured each visit. The same provider will activate the NiTi coil spring for retraction, along with data collection. Superimposition of scans will be utilized to assess outcome measures.

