## **13.0 Procedures Involved\***

**13.1 Provide a description of **all research procedures or activities** being performed and when they are performed once a subject is screened and determined to be eligible. Provide as much detail as possible.**

*NOTE: This should serve as a blueprint for your study and include enough detail so that another investigator could pick up your protocol and replicate the research. For studies that have multiple or complex visits or procedures, consider the addition of a schedule of events table in in your response.*

**Response:** Once the subject has been screened and been deemed eligible to participate in the study the following procedures will take place.

Standard of Care:

- Conventional Full Fixed appliances will be bonded to all permanent teeth (either 0.018" or 0.022" MBT prescription brackets), the maxillary canine bracket prescription will be 0.018" MBT (0.018" straight wire brackets MBT; 3M Oral Care, St. Paul, MN, USA)
- Phase of leveling and aligning will proceed through standard archwire progression, until 0.016 x 0.022" sized wire is able to be engaged.

- Sliding mechanics of canine retraction utilizing NiTi Closed Coil Springs to produce 150g of retraction force, utilizing the first molars and premolars as anchoring units.
- Correx Orthodontic Gauge will be utilized to verify 150g of force generation.

Research:

- A split mouth design will be utilized per patient, randomly assigning the upper left and right sides of the maxilla, through a random number generator.
- Split archwire design will utilize a crimpable binding mechanism to allow for joining of the SS and GUMMETAL wires together dividing at the junction of the maxillary central incisors.
- Patient's occlusion will be disclused to prevent interferences prior to retraction mechanics utilizing bite-turbos on the buccal inclines of the palatal cusps of the maxillary first molars.
- Intraoral scan will be taken utilizing an iTero intraoral scanner prior to beginning retracting mechanics on the upper canines (this will be timepoint T0).
  - Appointment date, patient name, age, sex and position of Canine T0 will be collected into the data sheet.
- If there is a need for absolute anchorage, miniscrews will be utilized on a per case basis.
- T1 will begin canine retraction on both side of the maxillary arch.
  - Intraoral scan will be done

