  - Data collection will be done: appointment date, patient name, position of Canine T1
- Each activation of the NiTi Closed Coil spring will be performed by the research examiner.
- After four weeks the patient will return for an adjustment visit:
  - Intraoral scan will be done
  - Data collection will be done: appointment date, patient name, position of Canine T2
  - Reactivation of retraction coil will be done
- After another four weeks the patient will return for an adjustment visit:
  - Intraoral scan and data collection will be done
  - This will mark T3 and reactivation of the retraction coil will be done by the research examiner.
- Final four weeks of retraction the patient will return for an adjustment visit:
  - Final intraoral scan, intraoral photographs, radiographs and data collection will be done marking T4 of data collection.
- There will be no more data collection following the T4 data collection point. The patient will continue orthodontic treatment per the treating resident's treatment plan agreed upon during the consultation.

- Data analysis will be performed by the researcher and statistician from the data collected from the patient.
  - Four consecutive digital models will be superimposed using 3-Shape analyzer software. Color-coded superimposition will be performed to verify the accuracy and precision of the superimposition.
  - To evaluate rate of canine retraction, total retraction distance and 3D tooth control, will be measured through the superimposition models
- Canine movement rate (mm/month) and total retraction distance (mm) will be assessed for the patient based on the position of the canine starting at T0 to T4.

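### Canine retraction is measured by two unreconciled routes, neither tied to a fixed reference, so movement of the anchor teeth could be counted as retraction

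*Combined protocol and SAP*

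**What the plan says.** The first primary objective in section 2.0 is: "Evaluate the total amount of canine retraction (mm) using GUMMETAL and Stainless-steel archwires". The second is the monthly rate of the same movement.

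Two accounts are given of how that movement is obtained.

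- **Section 6.1, space.** "Spaces will be measured at; T0 is initial records, T1 is initiation of space closure", and so on to T4. Then: "Space measurement and calculations will utilize 3Shape software to measure the distance of canine movement based off the distal surface". The canine's distal surface is named, but not the point from which it is measured.
- **Sections 6.1 and 13.1, superimposition.** Section 6.1 ends: "Superimposition of scans will be utilized to assess outcome measures". Section 13.1 says: "To evaluate rate of canine retraction, total retraction distance and 3D tooth control, will be measured through the superimposition models", and bases rate and distance on canine position from T0 to T4. The only quality check on the fit is: "Color-coded superimposition will be performed to verify the accuracy and precision of the superimposition". No registration region is named.

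On anchorage, 13.1 describes retraction "utilizing the first molars and premolars as anchoring units" and adds that, where absolute anchorage is needed, "miniscrews will be utilized on a per case basis". Section 13.2 lists canine position, rate and total distance as data. It lists neither space width nor the position of any anchor tooth.

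**The concern.** The space distal to the canine is bounded behind by the teeth that serve as anchorage. It narrows when the canine moves back and also when those teeth come forward. A figure taken from the space contains both movements. A figure taken from superimposed models separates them only if the models are registered on something the mechanics leave in place. If they are registered on the teeth, the moving teeth help to define the frame. A colour map shows how closely two surfaces match, not whether the matched surfaces have moved.

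The primary question is how far the canine itself travels on each wire, and the trial is sized for a 0.5 mm difference. Anchor movement of a few tenths of a millimetre, if it differed between sides, would matter on that scale. The listed data could not show whether it had occurred. The secondary outcome of three-dimensional control uses the same superimposition and shares the gap.

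**Working it through.** **Inputs from the protocol.** 16 patients, 80% power, significance level 0.05, difference 0.5 mm (20.2); paired t-test (20.1); three four-week intervals from T1 to T4 (6.1). The protocol gives no SD and no anchor-drift figure.

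**The plan's own figure.** Without an SD, 16 cannot be reproduced. Solving backwards for a two-sided paired t-test (noncentral t, 15 degrees of freedom, noncentrality 0.5 × √16 / SD), 80% power implies an SD of the within-patient difference of 0.667 mm, so the noncentrality is 0.5 × 4 / 0.667 = 3.0. This SD is an assumption used only to show scale.

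**Space route.** For each side let c be distal canine movement and a be mesial movement of the tooth behind the space.

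- Space closed on one side = c + a.
- Between-side difference = (c₁ − c₂) + (a₁ − a₂).

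If a₁ = a₂, the second bracket is zero and the comparison is unaffected, but each side's total is too large by a. For example, 0.3 mm of equal drift adds 0.3 mm to each total and 0.3 / 3 = 0.1 mm per four-week interval to each rate. If a₁ ≠ a₂, the difference enters one for one: with a true 0.5 mm, a drift difference of 0.25 mm gives 0.5 ± 0.25 = 0.25 or 0.75 mm, and 0.5 mm gives 0 or 1.0 mm.

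If the drift difference goes with the wire in every patient, and the paired SD is 0.667 mm:

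| Assumed drift difference (mm) | No true canine difference: chance of p ≤ 0.05 | True 0.5 mm, drift opposing: expected reading (mm) | Chance of p ≤ 0.05 |
|---|---|---|---|
| 0 | 5% | 0.5 | 80% |
| 0.1 | 9% | 0.4 | 61% |
| 0.2 | 20% | 0.3 | 39% |
| 0.3 | 39% | 0.2 | 20% |
| 0.5 | 80% | 0 | 5% |

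If the drift difference is unrelated to the wire, it adds variance instead. An SD of 0.2 mm raises the total SD to √(0.667² + 0.2²) = 0.70 mm and power falls to 77%. An SD of 0.5 mm gives √(0.667² + 0.5²) = 0.83 mm and 61%.

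**Superimposition route, if the fit used all the teeth.** The protocol does not say that it does. As an illustration, take 12 assumed crown centres and a rigid two-dimensional least-squares fit:

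| Canine movement (mm) | Anchor drift on the same sides (mm) | True difference | Reads |
|---|---|---|---|
| 2.5 / 2.0 | equal | 0.50 | 0.46 |
| 2.5 / 2.0 | 0.6 / 0.1 | 0.50 | 0.64 |
| 2.5 / 2.0 | 0.1 / 0.6 | 0.50 | 0.28 |
| 2.25 / 2.25 | 0.5 / 0 | 0 | 0.18 |

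The fit absorbs part of any left-right asymmetry as rotation of the model. That is why 0.50 reads 0.46 even with equal drift. It also misreads the level on each side: with no drift at all, 2.5 mm of canine movement reads about 2.1 mm.

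**Superimposition route, on a fixed reference.** The difference is c₁ − c₂, and none of these errors arises.

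**The case against.** The strongest reply is that 13.1 is the more specific section and settles the matter. It bases rate and distance on canine position on superimposed models, 13.2 lists canine position and no space width, and even the sentence in 6.1 names canine movement as its target. Sides are randomised, so drift unrelated to the wire adds noise rather than bias. Equal drift cancels in a paired space comparison. Miniscrews decided case by case may well be placed on both sides of the same patient. No document suggests that drift differs by wire, and every drift value above is assumed.

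Much of this stands. A reader might infer from 6.1 that the plan defines retraction as space closure, so that anchorage loss is certain to be counted. The documents do not support that: no section equates retraction with the reduction in space, and a stable registration would exclude anchor movement. Nor are the spaces limited to extraction sites; eligibility rests on bilateral space distal to the canines.

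The reply does not close the gap. Section 6.1 still makes space measurement the route to canine movement, and 13.1 helps only if the registration rests on something that stays still, which it does not say. Randomising sides does not remove a drift difference caused by the wire itself. Two teams could follow this text faithfully and obtain different primary outcomes.

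**Conclusion.** The point holds as follows: anchorage loss could be counted as retraction, because one stated route includes it by construction and the other leaves the reference open. It cannot be said that it will be counted, or that the between-wire comparison is biased in a known direction.

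Under a space measure, equal loss affects each side's mm and mm/month, and only a side-to-side difference biases the comparison. Under a fit on all the teeth, equal drift leaves a small attenuation (0.50 to 0.46 mm in the illustration), and the larger errors need a drift difference as big as the target effect. The sizes rest on assumed drift, an assumed arch and a back-solved SD.

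This is a cheap improvement to make before scanning begins, rather than a fatal flaw. Palate coverage cannot be added to a scan after the visit.

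**What to change.** In 6.1 and 13.1, reconcile the two accounts:

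- Define the primary outcome as antero-posterior displacement of the canine's distal surface from the start-of-retraction scan (T1, which both sections give as the start of retraction), in mm and mm/month.
- State that each later scan is registered to that scan on the palate (rugae and vault), not on the teeth. The protocol is silent on the reference. The palate is proposed because the springs act on teeth; its stability over the three four-week intervals is an assumption to state. Keep the colour map as a check of fit over that region.
- Drop space width as the measure of retraction.
- Require every scan to include the palate; 13.3 asks only for scans of the upper arch.
- Report mesial movement of the first molar by side, and miniscrew use by side, as descriptive data.

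The cost is protocol wording, slightly larger scans and one more measurement per side, with the same scanner and visits.

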***Describe other resources available to conduct the research.***

**17.2** *Describe the time and effort that the Principal Investigator and research staff will devote to conducting and completing the research.*

*NOTE: Examples include the percentage of Full Time Equivalents (FTE), hours per week. The question will elicit whether there are appropriate resources to conduct the research.*

**Response:** The time that will be allotted to research will be equivalent to 8 FTE hours per week. This time will be utilized to:

- Develop the appropriate archwire system to facilitate a split mouth design with the intervention and control group
- Collect, store and organize all records and data for each subject
- Perform necessary orthodontic adjustments for each patient
- Analyze data collected and work on the statistical analysis

**17.3** *Describe the availability of medical or psychological resources that subjects might need as a result of anticipated consequences of the human research, if applicable.*

*NOTE: One example includes: on-call availability of a counselor or psychologist for a study that screens subjects for depression.*

**Response:** The design of the study maintains minimal risk given that the orthodontic treatment is routine and there will not be a substantial increase in risk. All patients will have access to all resources they might need. If there are questions or concerns, they will have the Orthodontic department's emergency hotline, which will be able to route them to the appropriate individual that can help them. There are emergency procedures in place as well which they can access if necessary, during any time in the treatment. If the patient experiences

any psychological issues there are resources available which can easily be accessed.

*17.4 Describe your process to ensure that all persons assisting with the research are adequately informed about the protocol, the research procedures, and their duties and functions.*

**Response:** The entire protocol will be available in hard copy and electronic copy for anyone who will be involved in the research study. A streamlined version of the protocol will also be available for all who will be involved. There will be a presentation before patient recruitment commences to ensure that everyone who is involved can ask any questions and understands the workflow of the protocol. During this presentation, the duties and responsibilities of those who are involved will be explained and addressed.

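### The plan does not mask the scan reading to wire side, although one provider both activates the springs and collects the data, and lower GUMMETAL values are predicted

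*Combined protocol and SAP*

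**What the plan says.** **Who treats and who records.** Section 6.1: "The same provider will activate the NiTi coil spring for retraction, along with data collection". Section 13.1 names the role: "Each activation of the NiTi Closed Coil spring will be performed by the research examiner". The visit entries in the same section read "Data collection will be done: appointment date, patient name, position of Canine", so canine position goes onto the data sheet next to the patient's name.

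**What that person can see.** Section 13.1: "Split archwire design will utilize a crimpable binding mechanism to allow for joining of the SS and GUMMETAL wires together", with the join between the central incisors. The two alloys are in the same mouth, one on each side.

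**Who measures.** Section 13.1: "Data analysis will be performed by the researcher and statistician from the data collected from the patient". Listed beneath this are the superimposition and the statement "To evaluate rate of canine retraction, total retraction distance and 3D tooth control, will be measured through the superimposition models". The plan does not say whether this researcher is the examiner who treats. Section 17.2 lists "Perform necessary orthodontic adjustments for each patient" together with data collection and analysis as tasks of the research effort as a whole.

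**What is expected.** Section 3.2 predicts lower distance and rate with GUMMETAL, and section 4.0 words the endpoint as a decrease for GUMMETAL.

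**Safeguards named.** Section 13.1: "Color-coded superimposition will be performed to verify the accuracy and precision of the superimposition". Section 20.1 plans inter- and intraobserver intraclass correlations (ICCs). Section 20.3 has data de-identified and gives the research examiner, with supervisors, the data-quality check.

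The only use of the word blind in the available text is in the title of a cited study (reference 27).

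**The concern.** Both primary outcomes and the secondary outcome depend on someone placing landmarks and registering digital models. The plan itself treats this as observer-dependent, since it intends to report observer agreement. A reader who knows the side and expects less GUMMETAL movement may lean that way without intending to.

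The split-mouth design removes differences between patients. It does not remove a lean tied to wire side, because that lean points the same way in every patient whichever side was randomised to GUMMETAL. The listed safeguards do not address it either:

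- Colour-coded superimposition checks how well the models register.
- De-identification concerns identity and storage.
- ICCs measure agreement, and two observers with the same expectation can agree closely.

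At stake is whether a finding of lower GUMMETAL retraction, the predicted result, could be put down to the reading rather than the wire. Using one operator for all spring activations is sound standardisation and is not questioned.

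**Working it through.** **1. What the text establishes and what it leaves open.** Sections 6.1 and 13.1 together establish that the activating provider also collects data and is not shielded from side. Section 13.1 leaves the identity of the measuring researcher open. No available section masks the data collector, the reader or the analyst. Silence does not prove that the reading will be open, but an open reading would comply with the plan.

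**2. Which reading errors matter.** For one patient let D = (movement on the steel side) − (movement on the GUMMETAL side), where each movement is late position minus early position.

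- A constant landmark offset on a tooth appears in both the early and the late position and cancels within the side.
- A pure anteroposterior registration shift moves both canines equally and cancels between sides.
- A side-related lean that differs between early and late scans does not cancel: D observed = D true + b.

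Only the third kind is at issue.

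**3. Inputs.** Section 20.1: paired t-test, significance level 0.05 (sidedness not stated; two-sided assumed). Section 20.2: 16 patients, 80% power, 0.5 mm. The SD of D, the reading error and b are not given.

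**4. The plan's own figure.** N = 16 cannot be reproduced without an SD, so I solved for the SD that it implies under each paired reading:

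| Reading of section 20.2 | Implied SD of D (mm) |
|---|---|
| two-sided paired t | 0.667 |
| two-sided, normal approximation | 0.714 |
| one-sided paired t | 0.767 |
| one-sided, normal approximation | 0.804 |

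The range used below is 0.667 to 0.8 mm. Two-sample readings give a per-group SD and would also need a within-patient correlation, so they are left out.

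**5. False-positive rate with a lean b and no true effect.** The test statistic follows a noncentral t with 15 df and noncentrality (b/SD)·√16 = 4b/SD. The two-sided critical value is 2.131.

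Without assuming an SD:

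- The rejection rate reaches 10% at b/SD = 0.174 (4 × 0.174 = 0.70).
- It reaches 20% at b/SD = 0.297 (4 × 0.297 = 1.19).

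In millimetres these are 0.174 × 0.667 = 0.12 and 0.297 × 0.667 = 0.20. At SD 0.8 they are 0.14 and 0.24.

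| Assumed lean b (mm) | Two-sided rate, SD 0.667 | of which GUMMETAL lower | Two-sided rate, SD 0.8 | of which GUMMETAL lower |
|---|---|---|---|---|
| 0 | 5% | 2.5% | 5% | 2.5% |
| 0.02 | 5.1% | 3.2% | 5.1% | 3.1% |
| 0.05 | 5.9% | 4.7% | 5.6% | 4.2% |
| 0.1 | 8.7% | 8.1% | 7.6% | 6.8% |
| 0.2 | 20% | 20% | 16% | 15% |
| 0.3 | 39% | 39% | 29% | 29% |

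A simulation of 200,000 trials agreed for 0.1, 0.2 and 0.3 mm (8.7%, 20.3%, 39.2% at SD 0.667; 7.5%, 15.4%, 28.9% at SD 0.8).

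**6. Scale check.** The smallest observed mean difference that is significant is 2.131 × SD/4: 0.36 mm at SD 0.667 and 0.43 mm at SD 0.8. Leans of 0.1 to 0.3 mm do not by themselves produce a 0.5 mm difference. They act by moving chance results over the threshold.

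**The case against.** The strongest reply has four parts.

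**The reader may be someone else.** The sentence in section 6.1 is about standardising activation. The plan does not say that this provider makes the 3Shape measurements, and section 17.2 lists tasks for the team rather than for one person. This stands, and the point is limited accordingly: the reader is unnamed and unmasked, not shown to be the treating examiner. But section 13.1 asks for enough detail to replicate the study, and who reads the primary outcome, knowing what, is part of that.

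**Masking may be described elsewhere.** Some pages were not available for review. Section 23.2 points to a confidentiality section that is not in the supplied text, and section 13.3 mentions a data spreadsheet held separately. This limits confidence. It does not supply a masking rule.

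**De-identification may mask in part.** Side is randomised per patient, so a reader who cannot tell whose scan it is cannot look up the allocation, and the plan does not say that the alloys can be told apart on a scan. This is fair as far as it goes. However, section 20.3 gives no timing, the data sheet carries the patient's name, and someone who treated the patient may recognise the dentition.

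**The lean is hypothetical.** At 0.02 or 0.05 mm the effect is negligible (5.1% and 5.9% at SD 0.667). The background in section 5.1 is also favourable to GUMMETAL, so expectation could run the other way. Both points are correct. The concentration of errors in the predicted direction follows from assuming a lean in that direction. An opposite lean would distort the comparison equally, and masking protects against both.

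**Conclusion.** The concern holds, with medium confidence and moderate weight; the change should be made. The plan as written allows every outcome to be read by someone who knows the wire side and holds a stated directional expectation, and none of its listed checks is designed to hide the side. The actual bias cannot be sized from the documents. The rates of 10% at a lean of 0.17 SD and 20% at 0.30 SD rest on 16 analysed pairs, normally distributed differences, a two-sided 0.05 test and no true effect. The millimetre equivalents rest in addition on an SD of 0.667 to 0.8 mm inferred from section 20.2. The conclusion depends on none of these figures, only on the absence of a masking rule. It would be withdrawn if material not available here already provides for masked reading.

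**What to change.** Keep the single provider for spring activation. In sections 6.1 and 13.1, state which existing member of staff makes the primary measurements, and that these are made masked to wire side:

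1. Export scans under a study code, without name or allocation.
2. Crop or hide wire and brackets wherever they are visible.
3. Mirror a random half of the patients left to right, always all scans of a patient together so that superimposition is preserved. Someone other than the reader holds the key.
4. Lock the measurements before the allocation list is merged.

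The interobserver ICC in section 20.1 implies a second observer. If that person did not treat the patient, that person should make the primary reading; otherwise the examiner reads the coded scans. Naming the reader, coding the scans and locking the measurements are the core. Cropping and mirroring strengthen the masking and depend on what the software allows, which the plan does not say.

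**Cost.** Protocol wording and file preparation: 16 patients × 4 superimposed models = 64 scans, or 16 × 5 timepoints (T0 to T4) = 80, half of them mirrored. Treatment, visits and sample size do not change. For an unfunded study with 8 hours a week this is a real but modest task. Masking may be incomplete if the reader recognises the alloy or the dentition, especially if the treating examiner has to read, and the report should say so.
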